Cover Page

Official Title: Asthma and childhood obesity: Understanding potential mechanisms and identifying strategies to improve respiratory symptoms

NCT03586544

Date of Document: January 26, 2017

Updated: June 10, 2021

The 2013 American Thoracic Society guidelines strongly recommend interval warm-up exercise¹ to reduce EIB severity. This recommendation is based on studies of warm-up exercise protocols that reduce EIB severity in nonobese asthmatic children². However, no empirical data on the effects of interval warm-up exercise on EIB severity are available in *obese asthmatic children*, where excess fat exerts such an unfavorable burden on the respiratory system, particularly during exercise. Investigation of the effectiveness of *simple* EIB reduction strategies, such as interval warm-up exercise, in obese asthmatic children is urgently needed. Therefore, **the objective of this study is to investigate the effects of interval warm-up exercise on EIB in obese and nonobese asthmatic children.**

Our approach will be to investigate EIB after an exercise challenge test (ECT) preceded by a no-treatment control and two randomized conditions: (1) 8x30s interval warm-up and (2) pretreatment with a bronchodilator (short-acting beta agonist [SABA]). We will test the following aims in obese asthmatic children (n=12) compared with nonobese asthmatic children (n=12):

Aim: To investigate the effects of interval warm-up exercise on EIB severity

Hypothesis: Interval warm-up exercise will reduce EIB severity after an ECT to a similar extent as SABA and better than control.

RESEARCH STRATEGY

Study design and participants: This is a cross-sectional study. We will complete testing in 9 – 12 yr old nonobese and obese children with a physician diagnosis of mild asthma with a Tanner pubertal stage of ≤ 3 . This approach will enable us to study and compare obese and nonobese boys and girls of similar maturation while pubertal effects on lung function and exercise responses are minimized. For adequate power to test the stated hypotheses, 12 nonobese and 12 obese asthmatic children will need to complete all five visits in this study. We may need to enroll up to 50 children considering possible attrition, to reach a final sample of 12 obese and 12 nonobese asthmatic children.

All participants will have no history of smoking, no history or evidence of heart disease, no history of uncontrolled hypertension, no documented and/or diagnosed sleep disorders, no diagnosed diabetes, no metabolic disorders, no history of significant mental illness, no dietary restrictions, no serious health conditions, or no musculoskeletal abnormality that would preclude exercise. Children who have been hospitalized for an asthma exacerbation or who have taken oral glucocorticoids for asthma in the past year and children who have been admitted to an intensive care unit or been intubated because of their asthma in the past five years, will be excluded to reduce the risk of exacerbation during the study³.

BMI criteria: We will study nonobese children with a BMI between the 16th and 84th percentile and obese children with a BMI > 95 th percentile but less than 170% above the 95th percentile and less than an absolute BMI of $40 \text{ kg} \cdot \text{m}^{-2}$. Recently, there has been a shift towards classifying child BMI over the 95th percentile as a percent above the 95% percentile because the statistical procedures used to generate percentile curves are not accurate at the extreme tails of BMI distribution⁴. We have chosen 170% above the 95th percentile as a reasonable cut-off or upper-limit because it will exclude children with an average age and sex specific BMI of approximately $> 40 \text{ kg} \cdot \text{m}^{-2}$ (BMI Range 36 – 43 in boys and 37 – 45 in girls 9 – 12 yr), which roughly corresponds to Class III obesity in adults. Since this BMI percentile range also includes children with a BMI $> 40 \text{ kg} \cdot \text{m}^{-2}$, we will further exclude any children with an absolute BMI $> 40 \text{ kg} \cdot \text{m}^{-2}$.

Lung function criteria: We will study children with 1) FVC $\geq 80\%$ predicted, 2) FEV₁ $\geq 75\%$ predicted, and TLC $\geq 80\%$ predicted, consistent with normal pulmonary function and including participants with mild obstructive airway disease. Since the risk of severe EIB increases in children with moderate or severe obstructive airway disease, children with FEV₁ $< 75\%$ predicted will be excluded from the study⁵. Diagnosis of asthma (i.e., airway responsiveness with reversible obstruction) will be established by spirometry (i.e., improvement of FEV₁ of $\geq 8\%$ after administration of SABA⁶). Children without reversible airway obstruction will also be excluded from the study.

Aim: To investigate the effects of interval warm-up exercise on EIB severity

Introduction: The *working hypothesis* is that interval warm-up exercise will reduce EIB severity to a similar extent as a SABA and a greater extent than control in obese asthmatic children. Furthermore, we propose that reduction of EIB severity in obese asthmatic children after interval warm-up exercise and/or SABA may be to a lesser extent than in nonobese asthmatic children. The *rationale* behind the proposed research centers on the fact that

EELV will be forced to even lower levels during exercise in an obese asthmatic child creating the potential for increased airway hyperresponsiveness and EIB. In this context, interval warm-up exercise and SABA may improve EIB as it does in nonobese asthmatic children², but obesity-related changes in respiratory function may reduce the effectiveness of interval warm-up exercise and SABA in obese asthmatic children.

Sample size estimation: Our primary variable is maximum % fall in FEV₁ after interval warm-up exercise vs. no-treatment control. Schnall and Landau⁷ reported maximum % fall in FEV₁ after an exercise challenge preceded by interval warm-up of 6.9±5.2% compared to control 23.0±5.2%. Based on these data⁷, we would be able to detect a significant mean reduction in maximum % fall in FEV₁ between the control and interval warm-up at greater than 95% power in 12 nonobese asthmatic children. While effect sizes may be lower in obese asthmatic children, we can detect a maximum 9.9% fall in FEV₁ difference between control and interval warm-up at 80% power with a sample size of 12 obese asthmatic children. A sample size calculation to detect a significant group x treatment interaction was not possible for this aim without preliminary/published data. Nevertheless, testing the effectiveness of interval warm-up exercise on EIB in obese asthmatic children is itself of considerable clinical value and an important clinical outcome in the proposed project.

METHODS: Over five separate visits (1.5 – 2.5 h each), we will measure respiratory function, exercise tolerance, and EIB after an ECT that is preceded by a no-treatment control and two randomized conditions: (1) 8 x 30 s interval warm-up, and (2) pretreatment with a bronchodilator (SABA). Testing that requires physician oversight (e.g., exercise tests) will be conducted at the Sunrise Health and Medical Center (SHMC). Testing that does not require physician oversight, such as plethysmography measurements for lung volumes, will be conducted at UNLV.

Visit 1: We will conduct spirometry and airway resistance measurements (using FOT) before and after SABA (Albuterol 4 puffs, 90mcg per actuation) to assess airway hyperresponsiveness. Participants with an FEV₁ < 75% predicted will be excluded from the study to reduce risk of severe EIB after exercise⁵. Lung volumes (i.e., TLC, FRC, RV) will be measured by plethysmography. Maximal voluntary ventilation (MVV) will be determined from a 10 s test extrapolated to 1 min. Height, weight, circumference measurements (chest, waist, hip, and neck), and BMI percentile will be used to characterize body size and fat distribution.

Visit 2: Participants will undergo maximal graded cycle ergometry to exhaustion to measure exercise tolerance. Graded cycle ergometry will be performed using 1-min increments of 10W on an electronically braked cycle ergometer (VIAprint™, Vyaire Medical, Yorba Linda, CA). During cycle ergometry, we will measure ventilation and gas exchange to assess minute ventilation (V_E), $\dot{V}O_2$, $\dot{V}CO_2$, respiratory exchange ratio, and ventilatory equivalents for $\dot{V}O_2$ and $\dot{V}CO_2$. During cycle ergometry we will also measure exercise tidal flow-volume loops and participants will perform inspiratory capacity maneuvers by inhaling to TLC every minute to assess end-expiratory lung volume (EELV). Expiratory flow limitation (EFL) will be assessed by comparing overlap of exercise tidal flow-volume loops with the maximal flow-volume loop. For patient safety and to monitor progress during the test, we will also record ratings of perceived breathlessness (RPB: 0–10 scale), ratings of perceived exertion (RPE: 6–20 scale), blood pressure, heart rate, breathing frequency, tidal volume, pulse oximetry (SpO₂), and $P_{ET}CO_2$. $\dot{V}O_{2\max}$ will be confirmed by a supramaximal verification test at 105% of maximal work rate to exhaustion. Maximal exercise capacity will be evidenced by $\dot{V}O_{2\max}$ (highest $\dot{V}O_2$ obtained during maximal or verification test)⁸.

Visit 3: CONTROL VISIT We will ask participants to hold SABA for 8h, corticosteroid for 24h, and long acting asthma medications for 24h prior to the exercise challenge test (ECT) visits. Participants will also be asked to avoid exercise for 24h prior to the visit. We will measure FEV₁ using spirometry, airway function using FOT and FeNO before starting the ECT (see **Fig. 1** for timeline of ECT visits). The ECT will be performed in accordance with the American Thoracic Society guidelines⁵. Target work rate (W) will be calculated as $[(53.76 \times \text{measured FEV}_1) - 11.07]$ ⁵. Work rate will be increased from 60% of target work rate in the first minute, to 75% in the second minute, 90% in the third minute, and 100% in the fourth minute⁹. We will measure HR, SpO₂%, RPB,

and RPE during 6 minutes of cycling at 80-90% of HR_{max} . We will measure FEV_1 using spirometry and airway function using FOT at 2, 5, 10, 15, and 30min after completing the ECT (see **Fig. 1**). SABA will be administered to any patient with exercise-related respiratory symptoms and the test will be stopped. Spirometry and FOT measurements will be conducted every 5min after SABA administration to determine whether SABA effectively reversed the bronchoconstriction. A decision of whether to exclude the participant from the study will be made after consulting the pediatric pulmonologist.

Visits 4 and 5: ECT will completed 15 min after two randomized conditions: (1) 8 x 30 s interval warm-up and (2) pretreatment with a SABA. We will conduct spirometry and airway function measurements at baseline prior to after interval warm-up exercise or SABA administration. We will also conduct spirometry and airway function measurements at 2, 5, and 10 min after interval warm-up exercise or SABA administration and prior to the ECT to assess bronchodilation or bronchoconstriction resulting from interval warm-up and SABA. FeNO will

only be measured at baseline. ECT will be performed exactly as described in Aim 2. Details regarding interval warm-up and SABA administration are given below.

- Interval warm-up: eight 30 s intervals of cycling at 100% of the target work-rate calculated as $[(53.76 \times \text{measured } FEV_1) - 11.07]^5$. 45 s of active recovery at 20W will be performed between two intervals. The interval warm-up protocol selected for the proposed study was based on published research by Mickleborough *et al*¹⁰ comparing the effects of interval warm-up, SABA and no warm-up on EIB in nonobese asthmatic adults. We will monitor HR and SpO_2 during the test.
- SABA: 4 puffs of Albuterol (90mcg per actuation). Participants will actuate the medication into the spacer, inhale slowly from FRC and hold their breath for 10 s before exhaling. This procedure will be repeated four times with 1 min between actuations.

Statistical analysis plan: Comparisons in maximum % fall in FEV_1 from baseline will be made using a mixed ANOVA (between effect: obese, nonobese; within effect: control, SABA, interval warm-up). Pearson product-moment correlations will be utilized to examine associations between maximum % fall in FEV_1 and airway function (resistance and reactance) and FeNO, measures of body composition, and fat distribution.

[figure not shown]

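### The hypothesis that warm-up protects about as well as SABA has no criterion, no test that could support it and no power statement

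*Combined protocol and SAP*

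**What the plan says.** The hypothesis under the opening Aim has two parts: "Interval warm-up exercise will reduce EIB severity after an ECT to a similar extent as SABA and better than control". The Introduction to the Aim repeats both for the obese group, as the working hypothesis that "interval warm-up exercise will reduce EIB severity to a similar extent as a SABA and a greater extent than control in obese asthmatic children". Neither place defines what counts as similar.

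The Statistical analysis plan says that comparisons of maximum % fall in FEV₁ "will be made using a mixed ANOVA (between effect: obese, nonobese; within effect: control, SABA, interval warm-up"). The only other analysis is a set of Pearson correlations, which does not compare conditions.

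Under Sample size estimation the primary comparison is named: "Our primary variable is maximum % fall in FEV₁ after interval warm-up exercise vs. no-treatment control". The power claim for nonobese children (above 95%) and the detectable difference for obese children both refer to that comparison. Power for the group-by-treatment interaction is said not to be calculable. Yet Study design and participants states: "For adequate power to test the stated hypotheses, 12 nonobese and 12 obese asthmatic children will need to complete all five visits".

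**The concern.** A test of difference can reject equality but cannot establish similarity: a non-significant result is what one expects both when two treatments are alike and when there are too few children to separate them. Half of the stated hypothesis is a claim of similarity, and one of the three exercise-challenge visits is spent on SABA, but the plan does not say what result would support the claim or how a non-significant difference will be read.

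The risk is that no significant difference from SABA is reported as protection equal to SABA. That matters most in the 12 obese children, because the working hypothesis is stated for them and the opening section says no empirical data exist for this population. The statement on adequate power, which refers to hypotheses in the plural, adds to the risk because no power figure covers the SABA part.

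**Working it through.** **Inputs from Sample size estimation.** "interval warm-up of 6.9±5.2% compared to control 23.0±5.2"%, a benefit of 23.0 − 6.9 = 16.1 points; 12 children per group; and, for obese children, "we can detect a maximum 9.9% fall in FEV₁ difference between control and interval warm-up at 80% power".

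**Assumptions.** The documents give no SABA mean or SD, no within-child correlation r and no significance level, and do not say whether ± is an SD or a standard error. I take ± as an SD, a two-sided 5% level and a paired t-test.

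**The plan's own figure first.** The SD of the paired difference is SDd = 5.2 × √(2(1 − r)). For a 16.1-point difference with n = 12, power exceeds 99.9% for r from 0 to 0.9. The plan's statement of more than 95% is therefore consistent with its inputs.

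**SDs used for warm-up minus SABA.**

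- Low: r = 0.5, SDd = 5.2 × √1 = 5.2.
- Middle: r = 0, SDd = 5.2 × √2 = 7.35.
- High: 11.1, back-solved from the 9.9-point figure. With n = 12, 80% power needs a standardised difference of 0.889, and 9.9 / 0.889 = 11.1. This exceeds the maximum possible with two SDs of 5.2 (r = −1: 5.2 × √4 = 10.4), so it requires larger SDs in obese children.

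**Chance of a non-significant result when warm-up is truly worse than SABA** (noncentral t):

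| True deficit | n = 12: low / middle / high | n = 24 pooled: low / middle / high |
|---|---|---|
| 3 points | 55% / 75% / 86% | 23% / 52% / 76% |
| 5 points | 14% / 43% / 70% | 0.5% / 11% / 44% |
| 8 points | 0.2% / 7% / 38% | <0.1% / 0.1% / 8% |

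**95% CI half-width**, t × SDd / √n:

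- n = 12 (t = 2.201): 2.201 × 5.2 / 3.464 = 3.3; likewise 4.7 and 7.1 points.
- n = 24 (t = 2.069): 2.2, 3.1 and 4.7 points.

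**Smallest margin with 80% power to show warm-up not worse than SABA**, true difference zero, one-sided 2.5%:

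- n = 12: 4.6, 6.5 and 9.9 points, which is 29%, 41% and 61% of 16.1.
- n = 24: 3.1, 4.4 and 6.7 points.

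A two-sided equivalence test (two one-sided 5% tests) needs almost the same margins at n = 12: 4.7, 6.6 and 10.1 points (the last computed with SDd 11.2).

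**The case against.** The strongest reply is that the SABA comparison is secondary. The plan names warm-up against control as primary, shows openly which comparison was powered, and never says it will read non-significance as similarity. SABA is a level of the within-child factor, so the planned model can yield the warm-up minus SABA estimate and its interval. On this view the wording "to a similar extent as SABA" is an informal expectation in a 24-child study. Much of this stands: the primary comparison is untouched, and what is missing is a rule, not the data. But the phrase sits inside the stated hypothesis, and the power sentence covers the hypotheses collectively. If the phrase is only an expectation, the plan should say so.

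The figures can also be challenged:

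- If ± is a standard error, the low and middle SDs are too small and those columns too favourable.
- The high SD comes from a warm-up against control figure that does not reproduce from an SD of 5.2, so it is only an upper scenario.
- The mixed ANOVA's pooled error has (24 − 2) × (3 − 1) = 44 degrees of freedom. Assuming equal variances and sphericity, the n = 12 half-widths become 3.0, 4.3 and 6.5 points, and non-significance at a 5-point deficit becomes 10%, 37% and 67%. The change is modest.

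Finally, the Statistical analysis plan names no contrast at all, not even warm-up against control. That is true, but only the SABA part also lacks a criterion.

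**Conclusion.** The concern holds and should be fixed. The stated analysis does not answer the similarity half of the stated hypothesis, and the claim of adequate power is not shown for it. This conclusion follows from the text and depends on no assumed SD.

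The practical size does depend on the SD. At the low value the pooled comparison of 24 children is fairly informative; at the high value in 12 obese children it is not, since a true 5-point deficit would be missed about 70% of the time. It cannot be said that the sample is too small, because that needs a margin and an SD that the documents do not give.

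**What to change.** 1. In the Statistical analysis plan, name warm-up minus SABA in maximum % fall in FEV₁ as a contrast within each group, and pooled if wanted, and report its 95% CI.
2. Choose one of two courses before analysis:
   - Fix and justify a margin in points of maximum % fall, and claim similarity, in the sense of not worse than SABA by more than the margin, only if the upper limit lies below it. If similarity is meant in both directions, say so and require the interval to lie within the margin on both sides.
   - Reword the SABA comparison as estimation, and state that a non-significant difference will not be taken as similarity.
3. Limit the adequate-power sentence in Study design and participants to warm-up against control.

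The cost is a few sentences and one interval per group, with no new data or visits. The first course makes a similarity claim harder to reach with 12 children per group; the second gives up the formal claim.

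### The adequate-power claim covers similarity to SABA, which is not sized; and the 9.9-point figure for obese children is not the detectable difference that the stated inputs give if ±5.2 is an SD

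*Combined protocol and SAP*

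**What the plan says.** All places are in the combined protocol and SAP.

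- **Hypothesis (opening Aim):** "Interval warm-up exercise will reduce EIB severity after an ECT to a similar extent as SABA and better than control". The Introduction to the Aim repeats this for the obese group: "interval warm-up exercise will reduce EIB severity to a similar extent as a SABA and a greater extent than control in obese asthmatic children".
- **Study design and participants:** "For adequate power to test the stated hypotheses, 12 nonobese and 12 obese asthmatic children will need to complete all five visits".
- **Sample size estimation:** the primary comparison is maximum % fall in FEV₁ "after interval warm-up exercise vs. no-treatment control". The only numerical input comes from a cited study: "interval warm-up of 6.9±5.2% compared to control 23.0±5.2". From it the plan claims more than 95% power in 12 nonobese children. For the obese group it says "we can detect a maximum 9.9% fall in FEV₁ difference between control and interval warm-up at 80% power". It then discloses that "A sample size calculation to detect a significant group x treatment interaction was not possible for this aim without preliminary/published data".
- **Statistical analysis plan:** the treatment comparison is a "mixed ANOVA (between effect: obese, nonobese; within effect: control, SABA, interval warm-up" factor. No equivalence margin, confidence interval or planned contrast is mentioned.

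**The concern.** There are two gaps, and the second matters more.

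1. The 9.9 points is the only precision figure for the obese children, the group for whom the plan says no data exist. Read literally, it does not follow from the inputs beside it, so a reader cannot tell whether 12 children can detect about 5, 6.5 or 10 points.
2. The hypothesis has two halves: better than control, and similar to SABA. Only the first is sized. For the second there is no SABA mean or SD, no margin, no power and no expected precision. A mixed ANOVA tests for differences, so a non-significant warm-up vs SABA result in 12 children is weak evidence of similarity. A sentence claiming adequate power for the stated hypotheses invites the opposite reading.

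**Working it through.** **Inputs.** From Sample size estimation: means 23.0 (control) and 6.9 (warm-up), so a difference of 16.1; ±5.2 in each condition; n = 12 per group; 80% power. Not stated, so assumed: two-sided alpha 0.05, a paired t-test (noncentral t), and Y, the SD of within-child differences. If ±5.2 is an SD, Y = 5.2 × √(2(1 − r)), where r is the within-child correlation.

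**Step 1. The nonobese claim reproduces.** A paired test with n = 12 has 95% power at a standardised difference of 1.146. At 16.1 points, power therefore exceeds 95% for any Y below 16.1 / 1.146 = 14.0. The claim holds, but it is too permissive to reveal which Y was used.

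**Step 2. The 9.9 does not reproduce as a detectable difference.** For 80% power the standardised difference is 0.889, so the detectable difference is 0.889 × Y.

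| r | Y | Detectable at 80% power | Power at 9.9 |
|---|---|---|---|
| 0.5 | 5.20 | 4.6 | >99.9% |
| 0 | 7.35 | 6.5 | 98.8% |
| −1 (limit) | 10.40 | 9.2 | 85.1% |

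Even the mathematical limit falls short of 9.9.

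**Step 3. Where 9.9 might come from.**
- *Shrinkage allowance.* A two-sample t-test with 12 per arm and SD 5.2 detects 1.197 × 5.2 = 6.22 points. Then 16.1 − 6.22 = 9.88, which rounds to 9.9.
- *A larger SD of differences.* 9.9 / 0.889 gives Y of about 11.1, which the plan does not state.
- *±5.2 is a standard error.* With m subjects in the source study the SD is 5.2√m, and 9.9 then requires r of about 0.43 at m = 4, 0.62 at m = 6 or 0.81 at m = 12. The plan gives neither m nor r.

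**Step 4. Warm-up vs SABA within one group of 12.** The plan has no SABA data, so the same Y is assumed. The expected 95% CI half-width is t(0.975, 11) × Y/√12 = 2.201 × Y/3.464 = 0.635 × Y. The shortfalls of 3, 5 and 8 points are illustrations, not margins from the plan. The test is a paired contrast within the group.

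| Y | Half-width | Non-significant if truly 3 worse | 5 worse | 8 worse |
|---|---|---|---|---|
| 5.20 | 3.3 | 55% | 14% | <1% |
| 7.35 | 4.7 | 75% | 43% | 7% |
| 11.1 (only if 9.9 is literal) | 7.1 | 86% | 70% | 38% |

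**Step 5. Obese vs nonobese difference in benefit (control minus warm-up), 12 per group, equal Y.** The detectable difference at 80% power is 1.197 × Y = 6.2, 8.8 or 13.3 points for the same three values of Y. The 95% CI half-width is t(0.975, 22) × Y × √(2/12) = 0.847 × Y = 4.4, 6.2 or 9.4 points.

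**The case against.** - **The 9.9 may have a simple origin.** The 16.1 − 6.22 route uses only the plan's numbers and a conventional alpha. It also suits the context: the sentence opens by allowing for smaller effects in obese children, and it calls 9.9 a maximum, whereas a detectable difference is normally a minimum. This stands as a plausible explanation. A reader might infer that 9.9 has no basis in the plan or is simply wrong; neither is shown. But the text labels 9.9 as the control vs warm-up difference itself, the route ignores the pairing, and the match could be chance. The sentence needs correcting or sourcing either way.
- **Little turns on 9.9.** This is fair. If ±5.2 is an SD, 12 children have more than 80% power at 9.9. A reader might infer that the obese arm is too small for warm-up vs control; the documents do not support that.
- **The worst case depends on Y = 11.1.** Also fair. The 70% figure applies only if 9.9 is a literal paired detectable difference. With the plan's only spread figure read as an SD, the rate is 14% at r = 0.5 or 43% at r = 0.
- **The plan is partly open about its limits.** It names warm-up vs control as primary and says the interaction could not be sized. That deserves credit, but the disclosure does not extend to SABA similarity, and the sentence under Study design and participants carries no such limit.
- **Nothing says that non-significance will be taken as similarity.** True. Nor does the plan say how similarity will be judged.

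**Conclusion.** The point holds in two parts of unequal weight.

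**Main part.** Adequate power is claimed for hypotheses that include similarity to SABA, but only warm-up vs control is supported. For warm-up vs SABA, 12 children give an expected 95% CI of about ±3.3 to ±4.7 points for r between 0.5 and 0. A real 5-point shortfall would go undetected 14% to 43% of the time. These figures assume two-sided 5%, ±5.2 as an SD, and the same Y for the SABA contrast as for control. The claim is also broader than the plan's own statement on the interaction. This part is firm, because the missing margin, precision and power can be seen in the text.

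**Lesser part.** The basis of 9.9 is not stated, and under the SD reading it is not the detectable difference (4.6 to 6.5 points for r from 0.5 to 0, at most 9.2). The error, if it is one, is conservative for the primary comparison and changes no sample size.

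**What to change.** 1. **Sample size estimation.** The authors should confirm what 9.9 means. Replace the sentence with: with 12 obese children, a paired two-sided 5% test has 80% power for a mean difference of X points between control and warm-up, assuming an SD of within-child differences of Y (source). X = 0.889 × Y, which is 6.5 if SD 5.2 and r = 0 are adopted. Say whether ±5.2 is an SD or a standard error. If 9.9 was the allowable shrinkage, say so and recompute it with the paired formula: 16.1 − 6.5 = 9.6 at r = 0.
2. **Study design and participants.** Limit the adequate-power claim to warm-up vs control within each group.
3. **Statistical analysis plan.** Report warm-up minus SABA within each group, and the obese vs nonobese difference in benefit, as mean differences with 95% CIs. Give the expected half-widths (0.635 × Y and 0.847 × Y). State that a non-significant difference will not be read as similarity.

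The cost is a recalculation and three wording changes, with no extra children, visits or tests. The price is a narrower claim: similarity to SABA and the group comparison become estimates with intervals and are no longer presented as adequately powered tests.

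### How the warm-up/SABA order is generated and balanced within weight group is not stated, and the mixed ANOVA has no visit term, so a Visit 4 to 5 change costs precision and, if the order is uneven, shifts warm-up minus SABA and the group x condition interaction

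*Combined protocol and SAP*

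**What the plan says.** The Visits 4 and 5 paragraph of METHODS reads: "ECT will completed 15 min after two randomized conditions: (1) 8 x 30 s interval warm-up and (2) pretreatment with a SABA". The control test is not part of the randomisation; it has its own fixed place ("Visit 3: CONTROL VISIT").

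The Statistical analysis plan gives one model for the maximum % fall in FEV₁, a mixed ANOVA with "between effect: obese, nonobese; within effect: control, SABA, interval warm-up". It contains no visit, period or order term. No section describes the randomisation list, any blocking or stratification by weight group, or the point at which a child's order is assigned.

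Under Study design and participants, "12 nonobese and 12 obese asthmatic children will need to complete all five visits in this study", and "We may need to enroll up to 50 children considering possible attrition".

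The Sample size estimation paragraph defines the primary variable as the maximum % fall "after interval warm-up exercise vs. no-treatment control". Similarity of warm-up to SABA is part of the stated hypothesis, and a smaller benefit in obese children is proposed in the Introduction to the aim.

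**The concern.** Warm-up against SABA is the only comparison the trial randomises, and it does so through the order of two visits. Each child's warm-up minus SABA difference contains the treatment difference plus or minus any change between Visit 4 and Visit 5, such as habituation to the test, season or airway state. The sign depends on which condition came second.

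With no visit term, that change is treated as random error. If the two orders are not equally frequent among completers, part of it also stays in the estimate. If the imbalance differs between the weight groups, part of it enters the comparison of benefit between obese and nonobese children.

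A claim that warm-up works to a similar extent as SABA needs an unshifted estimate and a narrow interval, so this matters for a stated hypothesis even though it is not the primary contrast.

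**Working it through.** **Inputs from the documents.** 12 completers per group. Means and SDs behind the power statement: "6.9±5.2% compared to control 23.0±5.2"%, a difference of 23.0 − 6.9 = 16.1 points with SD 5.2 per condition. A detectable difference of 9.9 points at 80% power in 12 obese children.

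**Assumptions, because the documents are silent.** Two-sided 5% level. Visit 4 to 5 change D of 3 points in maximum % fall (range 2 to 5). Simple randomisation of order wherever a probability is given. SD of the within-child difference of 5.2 (which equals the per-condition SD only if the within-child correlation is 0.5) or 11.1.

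**The plan's own figures.** A paired t test with n = 12, difference 16.1 and SD of differences 5.2 has noncentrality 16.1/(5.2/√12) = 10.7. Power exceeds 99.99%, consistent with the stated figure of more than 95%. The 9.9-point figure does not follow from SD 5.2: the detectable difference is 4.6 points at correlation 0.5 and 6.5 at correlation 0. It does follow from an SD of differences of about 11.1, so that value is used as the second case.

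**Chance imbalance (Binomial(12, ½)).**
- 6:6 in one group: 0.226; in both groups: 0.226² = 0.051.
- 8:4 or worse: 0.388 in a given group; 1 − (1 − 0.388)² = 0.625 in at least one.
- 9:3 or worse: 0.146 in a given group; 1 − (1 − 0.146)² = 0.271 in at least one.
- With 12:12 forced overall but no stratification, 8:4 or worse within the groups still has probability 0.22 (hypergeometric).

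**Shift.** With n₂ children having warm-up second and n₁ first, warm-up minus SABA shifts by D(n₂ − n₁)/n.
- 6:6 gives 0, 8:4 gives D/3, 9:3 gives D/2. At D = 3 these are 0, 1.0 and 1.5 points.
- 8:4 in one group and 4:8 in the other shifts the group x condition contrast by D/3 + D/3 = 2D/3, or 2.0 points at D = 3.
- The overall obese vs nonobese effect shifts by 0, because every completer contributes both visits.

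**Precision for 12 children.** Under simple randomisation without a visit term, the difference has variance SD² + D². At SD 5.2 and D = 3 that is √(27.04 + 9) = 6.00, and the expected half-width is 2.201 × 6.00/√12 × 0.978 = 3.73 (0.978 is the mean of the sample SD relative to the true SD on 11 df). With 6:6 and a visit term, 10 df remain: 2.228 × 5.2/√12 × 0.975 = 3.26. A simulation using the contrast's own error term gave:

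| SD of differences | D | Simple randomisation, no visit term | 6:6 with visit term |
|---|---|---|---|
| 5.2 | 0 | 3.23 | 3.26 |
| 5.2 | 2 | 3.46 | 3.26 |
| 5.2 | 3 | 3.73 | 3.26 |
| 5.2 | 5 | 4.50 | 3.26 |
| 11.1 | 2 | 7.00 | 6.96 |
| 11.1 | 3 | 7.14 | 6.96 |
| 11.1 | 5 | 7.56 | 6.96 |

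**Type I error without a visit term, SD 5.2.** Averaged over simple randomisation it stays near 5%. Given a 9:3 split it is about 8%, 10% and 15% in that group at D = 2, 3 and 5. Given an exact 6:6 split the test is too conservative: about 2.5% at D = 3 and below 1% at D = 5. Balance alone is therefore not enough.

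**Coding of the visit term.** If Visit 4 = 0, Visit 5 = 1 and control = 0, the model treats control as if it sat at Visit 4. At 6:6 the variance of warm-up minus control is then multiplied by 1 + ¼ and its half-width by √1.25 = 1.12, about 3.1 to 3.4 points at SD 5.2, and its estimate moves by D/2. With −0.5, +0.5 and control 0 the half-width is essentially unchanged.

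**The case against.** The strongest reply is that the planned test of warm-up vs SABA is valid. Randomised order makes the bias zero on average, and type I error is near 5% under simple randomisation even with a 5-point visit effect. That stands. It limits the point to lost precision and to bias conditional on the split obtained, but the trial will obtain only one split.

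A reader might infer three stronger things, none of which the documents support.
- *That the order is unbalanced within weight group.* The documents are silent. The list could be blocked, and the binomial probabilities hold only if it is not.
- *That warm-up vs SABA absorbs the whole visit change.* It absorbs only the fraction (n₂ − n₁)/n, which is nil at 6:6.
- *That the obese vs nonobese comparison in general is contaminated.* A common visit change cancels from the overall group effect. Only the interaction, or a group comparison within one condition, is exposed, and the plan states that it could not calculate a sample size for the interaction.

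It is also fair that no visit effect is given in the documents, and that at SD 11.1 the gain at D = 3 is only 7.14 to 6.96 points, between 2% and 3%. The enrolment allowance of 50 is weak evidence of lost balance. Most of the stated exclusion points (lung function, reversibility, the decision described with the control test) come before Visit 4, and the documents do not say when the order is assigned.

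Finally, the primary contrast is warm-up vs control, which this point does not reach. What remains after all this is a randomised two-visit order analysed by a model that ignores the visits.

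**Conclusion.** The point holds as a recommended change, not as an error that invalidates the trial. The omission of a visit term is plain in the Statistical analysis plan. The absence of any stated balancing is a gap in specification, not evidence of imbalance.

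At an assumed visit effect of 3 points (range 2 to 5) and 12 children, the cost in half-width is 3.7 against 3.3 points at SD 5.2 (3.5 to 4.5 against 3.3). At SD 11.1 it is 7.1 against 7.0 (7.0 to 7.6 against 7.0). Under simple randomisation there is a 27% chance that at least one group is split 9:3 or worse, with a shift of at least half the visit effect in that group. The size rests wholly on the assumed visit effect, the SD of differences and simple randomisation.

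Control being fixed at Visit 3 is a separate matter. The primary contrast carries any change from Visit 3 to Visits 4 and 5, whatever is done about the order of those two.

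**What to change.** 1. Add visit to the condition model as a centred term: Visit 4 = −0.5, Visit 5 = +0.5, control = 0. Avoid 0/1 coding with control at 0, for the reason shown in the working.
2. If enrolment is open, state how the order is generated and draw it from permuted blocks separately for obese and nonobese children.
3. If enrolment is complete, report the order split among completers by weight group, and add the visit term.

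The cost is one degree of freedom. At 6:6 with no visit effect, the half-width for warm-up minus SABA rises by about 1% (3.23 to 3.26 points at SD 5.2). With an uneven split the term costs more, since the standard error is proportional to ½√(1/n₁ + 1/n₂): 3.46 points at 8:4 and 3.77 at 9:3, in exchange for removing the shift. No clinical procedure changes and no new data are needed.
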